## **9 Ethical Requirements**

### **9.1 Declaration of Helsinki**

The study will be performed in accordance with the applicable aspects of ISO 14155, recommendations guiding physicians in biomedical research involving human subjects adopted by the 18th World Medical Assembly, Helsinki, Finland (1964 and later revisions), ICH and US FDA GCP guidelines.

It is the responsibility of the Investigator to obtain approval of the study protocol from the IRB/EC and to keep the IRB/EC informed of any serious adverse event, serious adverse device effects, and amendments to the protocol. All correspondence with the IRB/EC should be filed by the Investigator and copies sent to the Sponsor or its designee.

### **9.2 Informed Consent**

The Investigator is responsible for ensuring that a completed informed consent is obtained in accordance with Section 6.5 of this protocol, as delegated by the site-specific Delegation of Authority, and according to country and local requirements.

### **9.3 Subject Data Protection**

Each subject will be assigned a unique subject identification number at the time of enrollment. This subject identification number will be retained throughout the study. Study sites will keep a log that notes the subject's name and corresponding subject identification number. All eCRFs will be tracked, evaluated, and stored using only the subject ID number. No personal identifying information will be included on the eCRFs.

The informed consent form will notify subjects that study monitors, Sponsor's representatives, auditors, and representatives of government agencies and ethics committees will have access to personal identifying information to ensure that data reported on the eCRFs corresponds to the person who signed the consent form and the information contained in the source documentation.

Each subject must be informed that the data collected will be stored and analyzed by computer and the applicable national regulations for handling of computerized data will be followed. Furthermore, each subject should be informed about the possibility of inspection of relevant parts of the hospital records by the Sponsor, or other Health Authorities, including the FDA; and that the data will be electronically stored in the United States.

## **10 Statistical Procedures**

### **10.1 General Statistical Considerations**

All confidence intervals presented will be two-sided. All statistical tests will be two-tailed with a significance level of 0.05. Descriptive statistics will be provided. This includes the number of observations, mean, median, standard deviation, inter-quartile range, minimum and maximum for continuous variables and counts and percentages for discrete variables. Analyses will be conducted using SAS (SAS Institute, Cary, NC). The specific details of the planned analyses are described completely in the statistical analysis plan.

### **10.2 Sample Size Estimation for the Primary Outcome**

The sample size calculations assume that 94% (108/115) of the study subjects achieve target limb salvage 1-month post-procedure as compared to 95.7% patients undergoing current standard of care treatments. Based on a binomial analysis with a non-inferiority margin of 10%, a study of 115 enrolled subjects will have 80% power with a one-sided alpha of 0.025. The sample size was adjusted to 130 subjects to account for approximately 10% attrition.

### **10.3 Control of Systematic Error and Bias**

The study will be conducted under a common protocol for each study site with the intention of pooling the data for analysis. Every effort will be made to promote consistency in study execution at each study site.

### **10.4 Missing Data and Imputation Methods**

Every effort will be made to keep all missing data, particularly at the 30-day follow-up visit, to a minimum. Some data may be missing, mainly due to lost-to-follow-up (LTFU)

subjects. The primary analysis will be data as observed. Sensitivity analysis will be performed.

## **10.5 Definition of Populations**

### **10.5.1 Screened**

Screened subjects are all subjects considered for participation in the study, whether or not they sign informed consent.

### **10.5.2 Screen Failure**

Screen failure subjects are all subjects considered for participation in the study, who failed to meet inclusion criteria or met exclusion criteria. Patients can be screen failed based on general criteria. These patients may or may not have signed an informed consent form.

### **10.5.3 Enrolled**

An eligible patient is considered enrolled once informed consent is obtained and Indigo Aspiration System has been inserted into the body.

### **10.5.4 Completed**

Completed subjects are all subjects who were enrolled and completed the study follow-up or were known to have died prior to the follow-up timepoint are considered completed. The completed subject metric will be provided for 365-day follow-up.

### **10.5.5 Early Termination**

Early termination subjects are all subjects who were enrolled but did not complete follow-up and were not known to have died are considered early termination subjects. The early termination subject metric will be provided for 365-day follow-up.

## **10.6 Definition of Analysis Populations**

### **10.6.1 Intent to Treat Sample**

As the primary analysis, all performance and safety outcome measures will be analyzed under the intent-to-treat (ITT) principle. Under this principle, the ITT sample includes all subjects who are enrolled. This population is the primary analysis population.

## **10.7 Interim Analysis**

No interim analyses are planned for the purpose of terminating the study for a positive result. Interim analysis without hypothesis testing may be performed for regulatory submission or publication of study results. No adjustments will be made to the confidence bounds for the final analysis.

## **10.8 Statistical Analysis of Primary Endpoint**

The primary endpoint is the target limb salvage rate at 1-month post-procedure. The primary safety analysis will be the difference between the study group and the combined historical control rate of 95.7% observed under current standards of care.

The null hypothesis is that the difference between the primary endpoint rate and the standard of care at 1-month post-procedure is less than or equal to -10%. The alternative hypothesis is the difference at 1-month post-procedure is greater than -10%. Formally, the null and alternative hypotheses to be tested are as follows:

$$H_0: P_{\text{study}} - 0.957 \leq -0.10$$

$$H_A: P_{\text{study}} - 0.957 > -0.10$$

Where  $P_{\text{study}}$  is the proportion of patients who achieve target limb salvage 1-month post-procedure.

The primary safety endpoint is met if the lower limit of the 95% confidence interval of the primary endpoint rate is greater than 85.7%. The primary safety analysis will be unadjusted.

## **10.9 Secondary Statistical Analysis**

The secondary performance and safety endpoints will be assessed via proportions based on the endpoint criteria and 95% confidence intervals will be presented. The modified SVS runoff score will be analyzed both as a categorical and a continuous outcome. Survival estimates will also be utilized to evaluate the time-to-event using Kaplan-Meier methodology for events through 365 days. With the date of procedure set at day 0, any event occurring on or before day 365 will be included.

## **10.10 Analysis of Adverse Events**

All adverse events will be summarized by showing the number and percent of subjects which report the event. Events will also be reported by relationship to the procedure or device. Adverse events judged as probably or definitely related to the Indigo Aspiration System will be analyzed as device-related.

## **10.11 Baseline Characteristics**

Baseline data including, but not limited to demographics, clinical characteristics, and angiographic characteristics will be summarized using descriptive statistics.

## **10.12 Pooling Across Centers**

Analyses will be presented by treatment group using data pooled across sites. Adjusted analysis using key baseline variables and the study site will be used to assess any potential site effects. This analysis will be performed on the intent-to-treat population.

## **10.13 Final Report**

A final report will be completed, even if the study is prematurely terminated. At the conclusion of the study, a multi-center abstract reporting the results will be prepared and may be presented at a major meeting(s). A multi-center publication may also be prepared for publication in a reputable scientific journal. The publication of results from any single center experience within the study is not allowed until the aggregate study results have been published, unless there is written consent from the Sponsor.

# **11 Study Committees and Core Labs**

## **11.1 Imaging Core Lab**

The Imaging Core Lab is composed of independent medical doctor(s) who are not participants in the study. The Imaging Core Lab is responsible for assisting in the development of specific criteria used for the categorization of clinical endpoints in the study. A web-based electronic database will be provided for the Imaging Core Lab to review and adjudicate images. Additional details related to the core lab are specified in the Imaging Core Lab Charter

The independent imaging core lab will review images from the pre-procedure and post-procedure (pseudonymized) angiograms to determine at minimum, the TIMI scores. An Imaging core lab charter will provide procedures for core lab review.

# **12 Study Administration**

## **12.1 Stopping the Study Based on Interim Safety Data**

The Medical Monitor will review periodic safety reports of all AEs and SAEs. The study can be temporarily suspended to evaluate any negative safety trends.

## **12.2 Clinical Study Termination/Withdrawal**

Subjects may be terminated or withdrawn from the study for the following reasons:

- Voluntary withdrawal of consent— meaning that a subject voluntarily chooses not to participate further in the study. All data collected up to the withdrawal of consent will be maintained in the study database. Withdrawn subjects will not have any additional follow-up and will not be replaced.
- Lost to follow-up — a subject will be considered lost-to-follow-up when contact is not achieved at the last required follow-up visit window. At a minimum, the effort to obtain follow-up information will include three (3) attempts to make contact via telephone or e-mail and if unsuccessful, then a letter from the Investigator sent via courier or other traceable method will be sent to the subject's last known address. These efforts to obtain follow-up will be recorded in the subject's study files.
- Subjects may also be withdrawn at the Investigator's discretion if within their best interest. A subject's participation in the clinical study will be terminated if the Investigator believes that this is in the subject's best medical interest or if the subject no longer complies with the clinical study requirements.

The sponsor may temporarily suspend or prematurely terminate the study at any time for the following reasons:

- Suspicion of risk to subjects
- If no positive IRB/EC decision is obtained or if the judgement of the IRB/EC is revoked
- If the applicable regulatory body has made an irrevocable objection
- If it transpires that continuation of study cannot serve any scientific purpose, and this is confirmed by the IRB/EC
- Business reasons

The Sponsor will document reasons for study suspension or premature termination and notify the PIs. The Sponsor will ensure that the IRB/ECs and regulatory authorities are notified in a timely manner.

The Sponsor will continue to provide resources to fulfil the obligations from the study protocol and existing agreements for following up the subjects enrolled in the study.

The Principal Investigators will promptly inform the enrolled subjects at his/her site, if appropriate.

If the Sponsor temporarily suspends the study and wishes to resume it, the Sponsor will inform the PIs, IRB/ECs, and (if appropriate) regulatory authorities. The Sponsor will provide a rationale for resuming the study. IRB/ECs must provide written approval before the study is resumed.

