### **12.3 Missing Visits**

Every effort should be made to bring subject in to scheduled follow-up visits. Any study subject who does not attend a scheduled follow-up visit should be contacted by site personnel to reschedule. If the missed visit was due to an adverse event, an AE eCRF must be completed and any reporting requirements met.

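### Protocol 12.2 lets a consenting subject be removed for non-compliance, nothing provides for collecting limb or vital status afterwards, and the SAP 11 imputations do not clearly cover the gap

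*Protocol*

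**What the plan says.** Protocol 12.2 introduces its reasons for leaving the study with "Subjects may be terminated or withdrawn from the study for the following reasons". The third reason begins by leaving withdrawal to the investigator's discretion and then turns mandatory: "A subject's participation in the clinical study will be terminated if the Investigator believes" this to be in the subject's best medical interest, "or if the subject no longer complies with the clinical study requirements". Non-compliance is a trigger of its own. It needs neither a medical reason nor withdrawal of consent, and the requirements in question are not defined.

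The only sentence on data after leaving belongs to the consent-withdrawal reason: "Withdrawn subjects will not have any additional follow-up and will not be replaced". Loss to follow-up is a separate reason: "a subject will be considered lost-to-follow-up when contact is not achieved at the last required follow-up visit window", with repeated contact attempts and a traceable letter required first.

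Other sections point towards keeping subjects and their data:

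- Protocol 12.3: "Any study subject who does not attend a scheduled follow-up visit should be contacted by site personnel to reschedule".
- Protocol 10.4: "Every effort will be made to keep all missing data, particularly at the 30-day follow-up visit, to a minimum".
- Protocol 10.6.1: "Under this principle, the ITT sample includes all subjects who are enrolled".

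On analysis, Protocol 10.4 makes the primary analysis as observed. If 30-day limb status is missing, SAP 11 adds a complete-data analysis and two imputations, limb lost and limb salvaged, for subjects lost to follow-up before 30 days. Secondary and subgroup analyses use complete data only. SAP 8.5 censors mortality at the last follow-up when later assessment is missing.

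**The concern.** The study treatment is one procedure on Day 0. What remains is scheduled follow-up alongside routine care, so for most subjects ceasing to comply can only mean ceasing to attend. A rule that ends participation on that ground removes subjects who still consent and whose key outcomes (amputation and its level, and death) could be learned without a clinic visit.

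If those who stop attending fare differently from those who stay, the missing outcomes are informative. It is easy to imagine them faring worse, for instance when readmitted elsewhere or moved into care. At stake are limb salvage at 30 days and 12 months and mortality at 12 months, in a single-arm study judged against a fixed threshold.

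**Working it through.** **Step 1. What happens to a subject ended for non-compliance.**

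| Place | Treatment of this subject |
|---|---|
| Protocol 10.6.1, SAP 7 | Stays in the ITT sample |
| Protocol 10.4, primary analysis | Not counted if 30-day limb status was not recorded |
| SAP 11, complete-data sensitivity analysis | Not counted, as in the primary analysis |
| SAP 11, limb-lost and limb-salvaged imputations | Unclear: they name only subjects lost to follow-up, a separate reason in Protocol 12.2 that rests on failed contact. A terminated subject may never have been out of contact |
| SAP 11, secondary endpoints, including 12-month limb salvage | Left out, with no missing-data sensitivity analysis |
| SAP 8.5, Kaplan-Meier mortality | Censored at last follow-up |
| Protocol 10.5.5, SAP 6.5 | Appears in the early-termination count only |

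The 30-day endpoint is touched only by terminations before limb status at day 30 is recorded. The 12-month endpoints are open to terminations throughout the year.

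**Step 2. The plan's own figures.** Inputs from SAP 3, Table 1: n = 115, threshold 0.957 − 0.10 = 0.857, assumed rate 0.94, one-sided alpha 0.025, null variance.

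Power = Φ{[(0.94 − 0.857) − 1.96·√(0.857·0.143/115)] / √(0.94·0.06/115)} = Φ{(0.0830 − 0.0640)/0.02215} = 0.805, as stated. The attrition allowance of about 10% of 130 is 13 subjects, leaving 117. This point disputes none of these figures.

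**Step 3. Illustration of bias at 30 days.** The documents give neither the number terminated (w) nor their salvage rate (s), so both are assumed. With 94% observed among the rest:

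rate in all enrolled = [0.94·(130 − w) + s·w] / 130

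| w | s = 75% | s = 60% |
|---|---|---|
| 7 | 93.0% | 92.2% |
| 13 | 92.1% | 90.6% |
| 20 | 91.1% | 88.8% |

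For w = 13 and s = 75%: (109.98 + 9.75)/130 = 92.1%. If the 13 all kept the limb, the same formula gives (109.98 + 13)/130 = 94.6%, so the sign depends entirely on s.

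**Step 4. Could such subjects decide the result?** The SAP 8.1 rule requires the lower limit of the two-sided 95% normal-approximation interval to exceed 85.7%. Take 117 observed and 13 missing.

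- As observed: 110/117 = 94.0%, lower limit 89.7%, passes.
- 13 counted as limb lost: 110/130 = 84.6%, lower limit 78.4%, fails.
- 13 counted as salvaged: 123/130 = 94.6%, lower limit 90.7%, passes.

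**Step 5. Chance of passing when the true all-enrolled rate is exactly 85.7%.** With 117 observed, the rule needs at least 107 salvaged. The rate among those observed is (0.857 − 0.1·s)/0.9. The exact binomial probability of passing is:

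- 4.3% if the missing subjects do not differ. The excess over 2.5% comes from the interval method, not from this point.
- 8.7% at s = 75% (observed rate 86.9%).
- 20.4% at s = 60% (observed rate 88.6%).

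**The case against.** The strongest reply is that the protocol, read as a whole, is milder than the one sentence. The list opens permissively and the preceding sentence leaves withdrawal to discretion. A reader might infer that a site must end participation after one missed visit. The documents do not support that: 12.3 answers a missed visit with rescheduling, and 7.6.4 does not list one as a reportable deviation. What stands is that 12.2 mixes permissive and mandatory wording without saying when repeated non-attendance becomes non-compliance.

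A reader might also infer that all later data, including adverse events, are certainly lost. The sentence ruling out further follow-up sits under consent withdrawal, and 7.6.1 collects events through final follow-up and asks for all deaths. The protocol is silent on limb and vital status after termination by the investigator. Loss of those data is the natural consequence, but it is an inference.

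Nor is the ITT definition breached. These subjects remain in the sample, and the problem is missing outcomes within it.

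SAP 11 does plan bounds for missing 30-day status, and if they were applied to these subjects the primary result would be bracketed. That reply stands except for the wording, which does not clearly reach them. It offers nothing for the 12-month endpoints.

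Finally, use of the clause may be rare: exclusion criterion 7 screens out patients unwilling or unable to follow the visit schedule. Nothing in the documents says how often it would apply.

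**Conclusion.** The concern holds as an inconsistency with avoidable consequences. Protocol 12.2 contains a mandatory sentence under which a consenting subject can be ended for poor attendance. It is in tension with 12.3 and 10.4, no provision secures limb or vital status afterwards, and the SAP imputations do not clearly include such subjects. The 12-month limb salvage and mortality endpoints are the most exposed.

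No bias can be estimated from the documents. The 92.1% against 94% example assumes that the whole all-cause attrition allowance of 13 is missing and that those subjects have 75% salvage. Consent withdrawal and ordinary loss to follow-up draw on the same allowance, so the example overstates what this clause alone would cause. A reader might infer from the table in the working that the observed rate is about 1 to 5 points too high in the device's favour. That follows from assuming salvage below 94% and, in its upper part, more attrition than planned. The direction is plausible, not proven. The limb-lost and limb-salvaged calculations show only that, at the planned attrition, the handling of missing subjects can decide whether the criterion is met.

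**What to change.** - **Protocol 12.2:** delete non-compliance as a reason to end participation. State that subjects who miss visits stay enrolled through day 365, with target-limb status (amputation yes or no, level, date) and vital status obtained by telephone or from the medical record unless consent is withdrawn.
- **SAP 11:** apply the limb-lost and limb-salvaged imputations to every enrolled subject with missing 30-day limb status, whatever the reason.

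The cost is a short amendment, one phrase in the SAP, and calls or chart checks for the subjects concerned, building on the contact steps already in 12.2. The consent form was not available for this review, so whether it already permits status checks from records should be confirmed. No treatment or clinical rule changes.

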### **12.3 Missing Visits**

Every effort should be made to bring subject in to scheduled follow-up visits. Any study subject who does not attend a scheduled follow-up visit should be contacted by site personnel to reschedule. If the missed visit was due to an adverse event, an AE eCRF must be completed and any reporting requirements met.

### **12.4 Protocol Adherence and Amendments**

Prior to beginning the study, the Principal Investigator must sign the protocol signature page documenting his/her agreement to conduct the study in accordance with this protocol. Deviations outlined in section 7.6.4 must be documented and reported to Penumbra as soon as possible, and to the IRB/EC per local guidelines and government regulations.

### **12.5 Study Registration**

The study will be registered in a publicly accessible trial study database (e.g., clinical trials.gov) prior to study initiation.

## **13 Publication of Information**

All information and data generated in association with this study will be held in strict confidence and remain the sole property of the Sponsor. The Investigator agrees to use this

information for the sole purpose of completing this study and for no other purpose without written consent from the Sponsor.

The results of this study may be offered for publication. The Investigators and the Sponsor shall collaborate in the writing of the study to ensure accuracy. All information not previously published concerning the test device and research, including patent applications, manufacturing processes, basic scientific data, etc., is considered confidential and should remain the sole property of Penumbra. The Investigator agrees to use this information only in connection with this study and will not use it for other purposes without written permission from the Sponsor.

## 16 APPENDIX I: Definitions and Classifications

### 16.1 Definitions

Acute Limb Ischemia:	Acute ( $\leq 14$ days), severe hypoperfusion of the limb characterized by these features: pain, pallor, pulselessness, poikilothermia (cold), paresthesias, and paralysis. 
Amputation:	The complete or partial removal of lower limb or extremity. Minor amputation is surgical removal of a portion or segment of the lower extremity distal or through the tarsometatarsal joints. Major amputation is complete or partial removal that occurs proximal to the tarsometatarsal joints. 
Limb Salvage:	Condition of extremity with potential to secure viability and preserve motor function to the weight-bearing portion of the foot if treated.  Limb is considered salvagable if amputation is performed at or distal to tarsal/metatarsal joint. 
Major Bleeding:	Fatal or leading to a drop in hemoglobin of $\geq 5$ g/dL, or significant hypotension with the need for inotropes, or requiring surgery (other than vascular site repair), or symptomatic intracranial hemorrhage (ICH), or requiring transfusion of two or three units of red blood cells or equivalent whole blood.
Minor Bleeding:	Bleeding that results in a drop in hemoglobin 3 to $< 5$ g/dL and/or that requires a blood transfusion of 1 unit of red blood cells or equivalent whole blood.
Modified SVS Runoff Score:	Calculated using the angiogram by assessing the patency and degree of stenosis/occlusion in the popliteal artery and the three tibial vessels. 
Nonviable Limb:	Condition of extremity (or portion of extremity) in which loss of motor function, neurological function, and tissue integrity cannot be restored with treatment. 
Patency:	Patency is defined as a target lesion without a hemodynamically significant stenosis/reocclusion on duplex ultrasound ( $> 50\%$ ,) and without target lesion reintervention (TLR).
TransAtlantic Inter-Society Consensus for the Management of Peripheral Arterial Disease (TASC II) Score	Used to classify vessel or arterial disease severity in the aortoiliac and femoropopliteal segments.

